## Table of Abbreviations

| Abbreviation or Term | Definition/Explanation                                    |
|----------------------|---|
| AE                   | adverse event   |
| ALL                  | acute lymphoblastic leukemia                              |
| alloHSCT             | allogeneic hematopoietic stem cell transplant             |
| ANC                  | absolute neutrophil count                                 |
| BiTE®                | bispecific T-cell engager                                 |
| CI                   | confidence interval                                       |
| CIVI                 | continuous intravenous infusion                           |
| CMV                  | Cytomegalovirus   |
| CNS                  | central nervous system                                    |
| CR                   | complete remission  |
| CRF                  | case report form  |
| CRh*                 | complete remission with partial hematological recovery    |
| CRi                  | complete remission with incomplete hematological recovery |
| CRS                  | cytokine release syndrome                                 |
| CSR                  | clinical study report                                     |
| CSF                  | cerebrospinal fluid                                       |
| CTCAE                | common terminology criteria for adverse events            |
| DLT                  | dose limiting toxicity                                    |
| DRC                  | data review committee                                     |
| DSMB                 | Data Safety Monitoring Board                              |
| ECOG                 | Eastern Cooperative Oncology Group                        |
| EOI                  | AEs of interest   |
| FAS                  | full analysis set   |
| HAMA                 | human anti-mouse antibodies                               |
| HSCT                 | hematopoietic stem cell transplant                        |
| ITT                  | intent-to-treat   |
| IV                   | Intravenous   |
| K-M                  | Kaplan-Meier  |
| MAD                  | maximum administered dose                                 |
| MedDRA               | Medical Dictionary for Regulatory Activities              |
| MRD                  | minimal residual disease                                  |
| MTD                  | maximum tolerated dose                                    |
| OS                   | overall survival  |
| PCR                  | polymerase chain reaction                                 |

---

| Abbreviation or Term | Definition/Explanation        |
|----------------------|-------------------------------|
| PD                   | pharmacodynamics              |
| PK                   | pharmacokinetics              |
| PPS                  | per protocol set              |
| PR                   | partial response              |
| R/R                  | relapsed/refractory           |
| RFS                  | relapse free survival         |
| SAP                  | statistical analysis plan     |
| TTHR                 | time to hematological relapse |
| ULN                  | upper limit of normal         |
| WHO                  | World Health Organization     |

## 1. Introduction

The purpose of this statistical analysis plan (SAP) is to provide details of the statistical analyses that have been outlined within the protocol for blinatumomab Study 20130265, **Amendment 5 (20 March 2019)**, entitled “A Phase 1b/2 Study of Blinatumomab in Japanese Subjects With Relapsed/Refractory B-precursor Acute Lymphoblastic Leukemia (ALL) (Horai Study)”.

The scope of this plan includes the interim analysis, the primary analysis, and the final analysis (**including expansion cohort**) that are planned and will be executed by Amgen’s Global Biostatistical Sciences department unless otherwise specified. Pharmacokinetics (PK) analysis will be provided by Department of Clinical Pharmacology, Modeling and Simulation (CPMS). Changes to the statistical analysis plan should be allowed to the extent that such deviations from the original plan would provide more reliable and valid analyses of the current data. Any “post hoc” or “data driven” analyses will be identified as such in the final clinical study report (CSR).

## 2. Objectives

### 2.1 Primary Objectives

Phase 1b

- To determine the maximum tolerated dose (MTD) of blinatumomab in adult and pediatric subjects with R/R B-precursor ALL.

Phase 2

- To further evaluate in adults the recommended dose identified in the Phase 1b portion of the study and to evaluate the rate of CR/CRh\* in adult subjects with R/R B-precursor ALL who receive blinatumomab.

### Expansion Cohort

- **To observe the incidence of treatment-emergent and treatment-related adverse events during treatment with blinatumomab in adult and pediatric subjects with R/R B-precursor ALL**

### 2.2 Secondary Objectives

Phase 1b

- To evaluate the safety, efficacy, pharmacokinetics (PK), and pharmacodynamics (PD) of blinatumomab in adult and pediatric subjects with R/R B-precursor ALL.

---

## Phase 2

- To evaluate other measures of efficacy, safety and PK in adult subjects with R/R B-precursor ALL at the blinatumomab regimen selected based on the Phase 1b data.

### Expansion Cohort

- **To evaluate the efficacy of blinatumomab in adult and pediatric subjects with R/R B-precursor ALL.**

## 3. Study Overview

### 3.1 Study Design

This is an open-label **combined** two-part multi-center clinical study to evaluate the efficacy, safety, and tolerability of blinatumomab in adult and pediatric Japanese subjects with R/R B-precursor ALL. The Phase 1b part will investigate the safety, efficacy, PK, and PD of blinatumomab to determine the MTD in adult and pediatric Japanese subjects respectively with R/R B-precursor ALL. In adult subjects, the Phase 2 part will assess the safety and efficacy of the recommended dose level of blinatumomab identified in the Phase 1b portion of the study in the adult study population. No phase 2 part is planned for the pediatric population in this study.

The study design for Phase 1b, Phase 2 **and Expansion** parts include:

- A 2-week Screening and Pre-Phase Period  
The pre-phase period within the screening period is permitted for the administration of dexamethasone to reduce tumor burden and the incidence of tumor lysis syndrome.
- Induction Phase  
Up to two induction cycles of blinatumomab. A single cycle of blinatumomab is defined as 6 weeks in duration, which includes 4 weeks of continuous intravenous infusion (CIVI) of blinatumomab followed by a 2-week treatment-free interval.
- Consolidation Phase  
Subjects who achieve a bone marrow response (blasts  $\leq 5\%$ ) within 2 induction cycles of treatment may continue to receive additional consolidation cycles of blinatumomab (up to a maximum of 5 total induction and consolidation cycles, or disease progression, intolerable adverse event or withdrawal of consent) under the same schedule as outlined in the induction treatment phase above.

- A safety follow-up visit is required 30 ( $\pm$  3) days after last dose of blinatumomab. Following the safety follow-up visit, subjects will be followed at 3, 6, 9, 12, 18, and 24 months ( $\pm$  2 weeks) after treatment start for disease **and survival status**. Subjects will return to the clinic for assessments until relapse, with the following exceptions:
  - Subjects who fail to achieve a bone marrow response (blasts  $\leq$  5%) within 2 induction cycles of blinatumomab treatment will undergo the safety follow-up visit and will be followed by telephone contacts in the long-term follow-up phase of the study.
  - Subjects who go on to receive allogeneic hematopoietic stem cell transplant (alloHSCT) or begin other treatment for ALL at any time following the first treatment cycle will undergo the safety follow-up visit and will be followed by telephone contacts in the long-term follow-up phase of the study.
- **For Expansion cohort, subjects will not be followed after safety follow-up visit. The subject will complete the study at the time of the safety follow-up visit.**

The overall study design is described by a study schema at the end of the protocol synopsis section.

### 3.2 Sample Size

The maximum sample size of 57 subjects (maximum of 36 for the Phase 1b part, 21 for the Phase 2 part) will be enrolled into this study. **Approximately 65 subjects (not restricted), including adult and pediatric subjects, may be enrolled in the expansion cohort.**

#### Phase 1b Part

No formal sample size estimation and statistical testing will be applied to the Phase 1b part of the study. The sample size for the dose finding phase of this study will be determined by the incidence and severity of adverse events in a rolling six Phase 1b design. For each population (adults and pediatric subjects), a minimum of 2 and up to 6 evaluable subjects will be enrolled at each dose level for determination of the dose to be selected for the Phase 2 efficacy part of the study, for a total of between 12 and 36 subjects.

#### Phase 2 Part

For the Phase 2 part of the study, the sample size estimation is based on the primary efficacy endpoint of hematological response. Simon's mini-max 2-stage design (Simon, 1989) is used with a sample size (13 subjects in the first stage, 21 evaluable

subjects total) based on a 1-sided type 1 error of 0.025 and a power of 90% to detect the effective response rate assumption of  $\geq 40\%$  over an ineffective treatment rate of  $\leq 10\%$ . The study will be stopped at the first stage if 1 or fewer out of 13 subjects are observed with CR/CRh\* in the first stage. If at least 6 or more out of 21 subjects show CR/CRh\* within 2 cycles of treatment with blinatumomab at the end of the second stage, one will be able to reject study's ineffective treatment assumption (refer to [Table 1](#)).

### **Expansion cohort**

For the expansion cohort of the study, the sample size is based on the enrollment rate in the Phase 1b and Phase 2 portion of the study in consideration of the expected time frame in which blinatumomab will be available in the commercial market in Japan.

**Table 1. CR/CRh\* Rates With Confidence Intervals for Phase 2 Part**

| Number of Subjects Reporting CR/CRh* at the end of cycle 2 | Observed CR/CRh* Rate (%) (N=21) | Exact 95% CI |
|--|----------------------------------|--------------|
| 5  | 23.8                             | (8.2, 47.2)  |
| 6  | 28.6                             | (11.3, 52.2) |
| 8  | 38.1                             | (18.1, 61.6) |
| 12   | 57.1                             | (34.0, 78.2) |
| 14   | 66.7                             | (43.0, 85.4) |

CR/CRh\* = complete remission/complete remission with partial hematological recovery.

## **4. Study Endpoints and Covariates**

### **4.1 Study Endpoints**

#### **4.1.1 Phase 1b Endpoints**

##### **Phase 1b Primary Endpoint:**

- Incidence of DLTs

##### **Phase 1b Secondary Endpoints:**

- CR/CRh\* within **first** 2 cycles of treatment with blinatumomab for adult subjects
- M1 remission within first 2 cycles of treatment with blinatumomab for pediatric subjects
- Duration of response (or Time to hematological relapse, TTHR)
- Relapse free survival (RFS)
- Overall survival (OS)
- Incidence and severity of adverse events

- Blinatumomab PK parameters (eg, steady state concentration [Css] and clearance of blinatumomab)
- Serum cytokine concentrations
- Incidence of anti-blinatumomab antibody formation

**Phase 1b Exploratory Endpoints:**

- Minimal Residual Disease (MRD) response
- Complete MRD response

**4.1.2 Phase 2 Endpoints**

**Phase 2 Primary Endpoint:**

- CR/CRh\* within 2 cycles of treatment with blinatumomab

**Phase 2 Secondary Endpoints:**

- Duration of response (or TTHR)
- RFS
- Allogeneic HSCT (alloHSCT) treatment with blinatumomab
- Best overall response within 2 cycles of treatment with blinatumomab
- OS
- Incidence and severity of adverse events
- 100-day mortality after alloHSCT
- Blinatumomab PK parameters (eg, steady state concentration [Css] and clearance of blinatumomab)
- Serum cytokine concentrations
- Incidence of anti-blinatumomab antibody formation

**Phase 2 Exploratory Endpoints:**

- MRD response
- Complete MRD response
- Peripheral blood lymphocyte subsets
- Neurological exam abnormalities and changes from baseline

**4.1.3 Expansion Endpoints**

**Expansion Primary Endpoint:**

- Incidence of treatment-emergent and treatment-related adverse events

**Expansion Secondary Endpoint:**

- **CR/CRh\* within first 2 cycles of treatment with blinatumomab for adult subjects**
- **M1 remission within first 2 cycles of treatment with blinatumomab for pediatric subjects**

**Expansion Exploratory Endpoint:**

- **MRD remission within first 2 cycles of blinatumomab**

**4.2 Planned Covariates**

Adult subjects and pediatric subjects will be summarized separately. Endpoints for adult subjects may also be described using the following subgroups as appropriate:

- Age ( $\leq 34$  yrs, 35-64 yrs,  $\geq 65$  yrs)
- Number of previous salvage therapies
- No prior HSCT, at least one prior HSCT
- Primary refractory or 1 relapse, 2 relapses, > 2 relapses prior to study entry
- Platelet counts at baseline (< 50,000; 50,000 to < 100,000;  $\geq 100,000/ \mu\text{L}$ )

Endpoints for Phase 1b part may not be described by the subgroup due to limited sample size. **Due to limited sample size endpoints for pediatric subjects will not be described by the subgroups.** Subgroup analyses will only be performed if there are at least two categories with at least 5 subjects in each of the categories.

**5. Hypotheses and/or Estimations**

**5.1 Phase 1b**

No formal hypothesis will be tested in Phase 1b part of the study.

**5.2 Phase 2**

The clinical hypothesis for the phase 2 part of the study is that blinatumomab will have clinical activity in the treatment of adult R/R ALL as measured by the rate of CR/CRh\* within 2 cycles. The study will test a null hypothesis that the level of clinical activity is an ineffective level of 10% or less. The assumed level of effective clinical activity is at least 40%.

**5.3 Expansion cohort**

**No formal hypothesis will be tested in Expansion cohort of the study.**

## 6. Definitions

### **Baseline**

Baseline is defined as the value taken on day 1 of the first cycle before start of infusion of blinatumomab. If such value is not available it may be replaced by the latest available value taken before start of the first blinatumomab infusion during the study.

### **Blast free hypoplastic or aplastic bone marrow**

For adult subjects:

Less than or equal to 5% blasts in the bone marrow, No evidence of disease, and insufficient recovery of peripheral blood counts: platelets  $\leq 50,000/\mu\text{L}$  and/or ANC  $\leq 500/\mu\text{L}$ .

For pediatric subjects, this treatment outcome will be considered as part of M1 remission.

### **Complete MRD response**

Complete MRD response is defined as having no detectable leukemia cells by PCR (**or flow cytometry**). Sensitivity and quantitative measurement range of assay need to be at least  $10^{-4}$ .

### **Complete remission (CR)**

CR is defined as  $\leq 5\%$  blasts in the bone marrow, no evidence of disease, and full recovery of peripheral blood counts: platelets  $> 100,000/\mu\text{L}$  and ANC  $> 1,000/\mu\text{L}$ .

### **Complete remission with partial hematological recovery (CRh\*)**

CRh\* is defined as  $\leq 5\%$  blasts in the bone marrow, no evidence of disease, and partial recovery of peripheral blood counts: platelets  $> 50,000/\mu\text{L}$  and ANC  $> 500/\mu\text{L}$  (but not a CR).

### **DLT observation period**

The time for the DLT assessment will be the first 14 days of treatment based on the observation that most adverse events are usually observed within a few days of treatment initiation and dose step. If the dose modification for pediatric subjects per [Table 2](#) is followed, time for the DLT assessment will be the first 21 days. An observed DLT will be attributed to the blinatumomab dose level administered at the time at which the DLT occurred.

**Table 2. Treatment Modification for Reversible CRS, Tumor Lysis Syndrome, and DIC**

| Current Dose              | Week 1                      | Week 2 (Day 8)            | Week 3-4 (Day 15)         |
|---------------------------|-----------------------------|---------------------------|---------------------------|
| 5 µg/m  /day  | 3.75 µg/m  /day | 5 µg/m  /day  | 15 µg/m  /day |
| 15 µg/m  /day | 5 µg/m  /day    | 15 µg/m  /day | 15 µg/m  /day |
| 10 µg/m  /day | 5 µg/m  /day    | 10 µg/m  /day | 10 µg/m  /day |

In addition, an incomplete treatment cycle with a treatment duration of less than 2 weeks will not be counted as an evaluable cycle for the primary endpoint and will have to be repeated (eg, if cycle 1 was interrupted on day 8 for more than 7 days, the next cycle will be denoted as cycle 1.1 and the same assessments will be performed as in cycle 1.)

**Dose limiting toxicity (DLT)**

A DLT will be defined as follows:

- Any CTCAE grade  $\geq 3$  adverse event related to blinatumomab, with exceptions noted below.
- Persistent CTCAE grade  $\geq 2$  non-hematologic adverse events related to blinatumomab that are deemed intolerable by the subject or the treating physician that do not respond to appropriate medical management within 5 days and lead to treatment discontinuation.
- Non-hematologic or non-infection adverse events related to blinatumomab leading to treatment discontinuation lasting  $>14$  days are to be considered DLTs by the DRC

The following will not be considered DLTs:

- Specific CTCAE grade  $\geq 3$  adverse events considered to be consistent with the current known safety profile of blinatumomab.
- CTCAE grade  $\geq 3$  fever or infection.
- Laboratory parameters of CTCAE grade  $\geq 3$  not considered clinically relevant and/or responding to routine medical management.

**End of study for individual subject**

Defined as the last day that protocol-specified procedures are conducted for an individual subject.

**Hematological Relapse (HR)**

For adult subjects:

Proportion of blasts in bone marrow  $> 5\%$  or blasts in peripheral blood after documented CR/CRh\* during the study.

For pediatric subjects:

Proportion of blasts in bone marrow > 25% following documented M1 remission.

An extramedullary relapse will be considered as a relapse event. The relapse may be subdivided in CD19 positive and CD19 negative relapses if available.

### **Hypocellular or acellular bone marrow**

For pediatric only:

Not achieve M1 bone marrow status, no evidence of disease, and Insufficient recovery of peripheral blood counts: Platelets  $50 \times 10^9/L$  and/or ANC  $\leq 0.5 \times 10^9/L$

### **M1 remission**

For pediatric subjects only: M1 remission is defined as  $\leq 5\%$  blasts (M1 bone marrow) in the bone marrow and no evidence of disease.

### **Maximal administered dose (MAD)**

The MAD to be tested for this study is  $28\mu g/day$  for adults and  $15 \mu g/m^2/day$  for pediatric subjects.

### **MRD progression**

Increase in the MRD level by one log as compared to the baseline level which is equal to a 10-fold increase in the number of MRD cells.

### **MRD relapse**

For adult subjects: Re-appearance of leukemic cells detectable by PCR (**or flow cytometry**).

For pediatric subjects: Increase of MRD level from last assessment by at least 1 log following an MRD response.

### **MRD response**

MRD  $< 10^{-4}$  measured by PCR (**or flow cytometry**).

### **Non-response**

For adult subjects only: None of CR, CRh\*, CRi, Blast free hypoplastic or aplastic bone marrow, Partial Remission or Progressive Disease.

### **Overall survival (OS)**

OS will be calculated relative to the start date of blinatumomab infusion in the first treatment cycle. All deaths will count as events on the date of death.

Patients alive will be censored on the last documented visit date or the date of the last phone contact when the patient was last known to have been alive. For patients who have withdrawn their informed consent, only information until the date of withdrawal will be used for analysis.

As a sensitivity analysis, OS may also be measured whereby survival will be censored at the time of HSCT.

### **Partial Remission (PR)**

For adult subjects:

Bone marrow blasts **> 5% - < 25%** with at least a 50% reduction from baseline

For pediatric subjects: complete disappearance of circulating blasts, achievement of M2 **bone** marrow status (**>5%** to **< 25%** blast cells), and appearance of normal progenitor cells.

### **Progressive Disease (PD)**

PD is defined as the followings:

**For adult subjects**, an increase from baseline of at least 25% of bone marrow blasts or an absolute increase of at least 5,000 cells/uL (whichever is greater), in the number of circulating leukemia cells.

**For Pediatric subjects**, an increase from baseline of at least 25% or an absolute increase of at least 5,000 cells/uL (whichever is greater), in the number of circulating leukemia cells, development of extramedullary disease, or other laboratory or clinical evidence of progressive disease.

### **Relapse-free survival (RFS)**

RFS is defined for subjects who achieved a response (CR/CRh\* for adult subjects or M1 remission for pediatric subjects) during the induction phase. It will be calculated relative to the date of bone marrow aspiration when response (CR/CRh\* for adult subjects or M1 remission for pediatric subjects) was detected for the first time during the induction phase. The date of bone marrow aspiration at which hematological relapse was first detected or the date of diagnosis on which the hematological or extra medullary relapse was documented or the date of death due to any cause will be used as the event date for relapse-free survival, whichever is earlier.

A patient who did not experience hematological relapse and did not die will be censored on the date of the last available bone marrow aspiration prior to data cutoff date of analysis.

As a sensitivity analysis, RFS may also be measured whereby censoring will occur at the time of HSCT.

### **Stable disease (SD)**

For pediatric patients only: fail to qualify for M1 remission, PR or PD.

### **Study completion**

#### **Phase 1b/2**

Patients who **have** completed the scheduled visits of induction **and consolidation** phase, **safety follow-up** and **long-term** follow-up period are deemed as study completion.

#### **Expansion cohort**

**Patients who have completed the scheduled visit of induction and consolidation phase and safety follow-up period are deemed as study completion. Long-term follow-up is not required for subjects participating in expansion phase.**

### **Study day 1**

Defined as the first day that protocol-specified investigational product(s)/protocol required therapies is/are administered to the subject.

### **Duration of response (or Time to hematological relapse, TTHR)**

The Duration of response will be calculated relative to the date of bone marrow aspiration when response (CR/CRh\* for adult subjects or M1 remission for pediatric subjects) was detected for the first time during the induction phase. Patients with response who did experience hematological relapse or PD, the end date of duration will be based on:

- the date of bone marrow aspiration at which hematological relapse or PD was first detected,
- the date of diagnosis on which the hematological or extra medullary relapse was documented,
- the date of death if patient died due to PD
- the date of end of induction phase if primary reason for treatment termination was hematological or extramedullary relapse

whichever is earlier and considered as reporting an event.

For a responder who did not report an event and was alive during the study, the end date of duration (censoring) will be based on the date of the last available bone marrow aspiration prior to data cutoff date of analysis.

Patients with response who did not report an event and did die due to other reason, the end date will be the date of death. Such deaths will be treated as competing risks in the analysis ([Hosmer, Lemeshow, and May, 2008](#)) using cumulative incidence function method when appropriate.

As a sensitivity analysis, duration of response may also be measured whereby censoring will occur at the time of HSCT.

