**Table 4. Efficacy Endpoint Summary for Phase II (Adults Only)**

| Phase II Endpoint                | Primary Summary and Analysis Method  | Sensitivity Analysis   |
|----------------------------------|--|--|
| Primary Endpoint                 |  |  |
| CR/CRh*                          | 
 
Summary statistics of CR/CRh* rate within first 2 cycles. The rate will be estimated along with its 95% exact CI. FAS subjects without response assessment will be treated as non-responders.
 
                | 
 
Repeat the analysis for subjects in the FAS who had non-missing post-baseline response data.
 
May repeat the analysis for PPS when deemed appropriate.
 
 |
| Secondary Endpoints              |  |  |
| Duration of Response (or TTHR)   | 
 
FAS subjects who achieved CR/CRh* in first 2 cycles are included.
 
Cumulative incidence function considering competing risk will be provided when sample size is appropriate.
 
                 | 
 
Censoring at the time of HSCT may be considered as deem as appropriate.
 
  |
| Received AlloHSCT                | 
 
Summary statistics of proportion of AlloHSCT in FAS.
 
   |  |
| Best overall response (ORR)      | 
 
Summary statistics of ORR within first 2 cycles. FAS subjects without response will be included.
 
The rate will be estimated along with its 95% exact CI.
 
  | 
 
Additional sensitivity analysis will be conducted and will exclude those subjects without any post-baseline response assessment.
 
                               |
| Overall survival                 | 
 
FAS subjects will be used
 
K-M estimates will be used and 3, 6 and 12 months rates will be provided.
 
  | 
 
Censoring at the time of HSCT may be considered as deem as appropriate.
 
  |

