**10.6.2 Analyses of Secondary Efficacy Endpoint(s)**

When sample size is deemed appropriate (ie, at least 10 subjects), RFS and OS will be summarized by K-M method. Duration of response (or TTHR) will be estimated by the

nonparametric methods for estimating cumulative incidence function by treating the death not due to PD as a competing risk (Hosmer, Lemeshow, and May, 2008). OS will be performed on FAS and the event time will be calculated relative to the start date of blinatumomab infusion in the first treatment cycle. RFS and Duration of Response (or TTHR) will include subjects in the FAS who achieved CR/CRh\* (for adult subjects) or M1 remission (for pediatric subjects). The event time will be calculated relative to the date of bone marrow aspiration when response was detected for the first time in this study. For RFS and OS, three, six and twelve month survival rates will be provided. Additional summary considering the censoring at the time of HSCT may be considered for the sensitivity analysis purpose.

Proportion of subjects who undergo alloHSCT in remission due to treatment with blinatumomab will be summarized based on FAS. Subjects who receive an HSCT later during the long-term follow-up time of the study will be reported separately.

**When sample size is deemed appropriate**, the analysis of 100-day mortality after alloHSCT will be based on FAS with alloHSCT while in any CR following treatment with blinatumomab. The 100-day mortality rate after alloHSCT will be estimated by taking 1 minus the K-M survival proportion at day 100 on the subset of subjects who undergo an alloHSCT in the FAS.

**Secondary efficacy endpoints for expansion cohort in the study is CR/CRh\* for adult subjects or M1 remission for pediatric subjects within the first 2 cycles of blinatumomab treatment. Analysis of these endpoints based on Expansion analysis set (EAS) will be the same as for primary efficacy endpoints in phase 2.**

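### As written, the SAP's TTHR rule dates a relapse that ends treatment in consolidation to the end of induction, while RFS uses the actual relapse date

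*SAP*

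**What the plan says.** SAP Section 6, under Duration of response (or TTHR), starts the clock at the marrow aspirate on which response "was detected for the first time during the induction phase". For a responder who relapses or progresses, it lists four candidate end dates:

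1. the aspirate first showing relapse or progression;
2. the date on which a hematological or extramedullary relapse was diagnosed;
3. death from progression;
4. "the date of end of induction phase if primary reason for treatment termination was hematological or extramedullary relapse".

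The selection rule is "whichever is earlier and considered as reporting an event".

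The RFS definition in the same section has the same starting point. Its event date is "The date of bone marrow aspiration at which hematological relapse was first detected or the date of diagnosis on which" relapse was documented, or death from any cause, whichever comes first. It has no end-of-induction item.

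SAP Section 3.1 describes induction as "Up to two induction cycles of blinatumomab", followed by consolidation for marrow responders, to a maximum of five cycles in all. Protocol Sections 6.6 and 8.3 make relapse after a marrow response a reason to stop treatment, with no restriction to one phase.

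SAP Table 4 limits the Phase 2 TTHR analysis to subjects "who achieved CR/CRh* in first 2 cycles" and adds: "Cumulative incidence function considering competing risk will be provided when sample size is appropriate". Protocol Sections 10.4.1 and 10.4.3 give TTHR no end-of-induction event date, and SAP Section 11 does not list one as a change from the protocol.

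**The concern.** The trigger for the fourth date is that treatment stopped because of relapse. It does not require that treatment stopped in induction, and it is not reserved for subjects with no relapse date on file. A responder taken off consolidation for relapse meets the trigger. The end of induction then always precedes the relapse, so taking the earliest date always selects it. The event is placed at a time when the subject was still in remission.

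Three things follow. TTHR is too short for these subjects. TTHR and RFS disagree on the same relapse, although both start from the same aspirate and should coincide when the first event is a relapse. And because no date is assigned to the end of the induction phase, two programmers could code it differently.

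**Working it through.** The documents give no figure that depends on this rule, so there is nothing to reproduce. The check applies both definitions literally.

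**Inputs**
- Cycle length 42 days; induction up to two cycles; at most five cycles in total (SAP Section 3.1).
- Marrow on day 29 of every cycle (Protocol Table 6, footnote e).
- Assumptions: no delays; two induction cycles given; induction ends somewhere between cycle 2 day 29 and cycle 2 day 42, since the SAP gives no date.

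**Study days**, from 42 × (cycle − 1) + day:
- cycle 1 day 29 = 29
- cycle 2 day 29 = 42 + 29 = 71
- cycle 2 day 42 = 42 + 42 = 84
- cycle 3 day 29 = 84 + 29 = 113
- cycle 4 day 29 = 126 + 29 = 155

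**Formulas**
- RFS = relapse day − response day
- TTHR as written = min(relapse day, end-of-induction day) − response day
- Back-dating = RFS − TTHR = relapse day − end-of-induction day, for any relapse after induction

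| Relapse found | Response found | RFS (days) | TTHR, induction ends day 84 | TTHR, induction ends day 71 | Back-dating (days) |
|---|---|---|---|---|---|
| Cycle 3 day 29 (113) | Cycle 1 (29) | 84 | 55 | 42 | 29-42 |
| Cycle 3 day 29 (113) | Cycle 2 (71) | 42 | 13 | 0 | 29-42 |
| Cycle 4 day 29 (155) | Cycle 1 (29) | 126 | 55 | 42 | 71-84 |
| Cycle 4 day 29 (155) | Cycle 2 (71) | 84 | 13 | 0 | 71-84 |

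TTHR as written does not depend on when in consolidation the relapse occurred. For a cycle 2 responder it can be zero.

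**Sensitivity.** Induction is up to two cycles. If a cycle 1 responder's induction is taken to end with cycle 1 (day 29 to 42), the back-dating is larger: 113 − 42 = 71 to 113 − 29 = 84 days for a cycle 3 day 29 relapse, and 155 − 42 = 113 to 155 − 29 = 126 days for cycle 4 day 29.

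**Not affected.** A relapse during induction already precedes the end of induction. A relapse after treatment stopped for another reason does not meet the trigger. Nor, probably, does one found at the end of cycle 5, because treatment then ended by completion. An isolated CNS relapse with treatment continued is also outside it.

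**The case against.** The strongest reply is that the phrase is stale wording for end of treatment. SAP Table 6 (Section 10.7.6) starts follow-up medication the day after the end-of-induction visit and does not mention consolidation. In the definitions of study completion and of treatment-emergent events, the words covering consolidation and the treatment period are in bold, like other text that appears new in this SAP version. The TTHR item and Table 6 may simply have been overlooked. The literal result is also odd enough to be queried: entry to consolidation requires a marrow response, so relapse would be dated to about when the subject qualified as responding. This is plausible, and on that reading the back-dating is essentially nil. But it is inference. The same definition uses the phrase for the window in which response is first detected, which Table 4 gives as the first two cycles, and Section 3.1 describes induction as at most two cycles.

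The second reply is limited reach, and it stands. TTHR is secondary and descriptive, and is shown only if numbers allow. The one numerical threshold, "When sample size is deemed appropriate (ie, at least 10 subjects), RFS and OS will be summarized by K-M method", is not stated for TTHR. TTHR is not among the endpoints that Protocol Section 10.3.5 lists for update at the final analysis. The primary analysis is triggered by completion of Phase 2 induction (Protocol Section 10.3.4), so some consolidation relapses may not be in its data. The SAP change log says Table 4 was aligned with the report of the primary analysis, so TTHR has probably been derived already. RFS would show the true relapse dates beside it, and the error shortens duration, so it cannot flatter the drug.

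A reader might infer that a sizeable share of responders is misdated, for example from the 5.9-month median RFS that the protocol cites from another study. The documents do not support such a count. That median includes deaths, and a model based on it would also count subjects who stopped for other reasons or went to transplant. The rule applies only where relapse was the main reason for stopping during consolidation, and no document gives that frequency.

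**Conclusion.** The rule is wrong as written, and the severity is minor. Read literally, it back-dates a relapse that ends consolidation by 29-42 days (cycle 3 day 29) or 71-84 days (cycle 4 day 29), and contradicts RFS for the same relapse. These sizes rest on 42-day cycles without delay and two induction cycles ending between days 71 and 84. If end of treatment was intended, the fault is only in the wording, but the sentence still needs correcting. That the literal text gives the wrong date is clear; whether it was programmed that way is uncertain. The CR/CRh* test, RFS as written and OS are unaffected, so the point does not bear on the trial's main efficacy conclusion.

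**What to change.** - In the TTHR definition, replace the fourth item with the date of treatment termination, used only when termination was for relapse and neither a marrow date nor a diagnosis date of relapse is recorded. Deleting the item is not enough: Protocol Section 6.6 waives the marrow when progression is documented, so a subject stopped for relapse with no recorded relapse date could be censored at the last marrow.
- Add the same fallback to the RFS definition. It has none now, so such a subject, if alive, would be an event for TTHR and censored for RFS. State that both endpoints use one date per relapse.
- Align the end-of-induction wording in SAP Table 6.
- Confirm how TTHR was derived for the primary analysis, and re-run it if the end-of-induction date was used.

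The cost is two SAP definitions, the Table 6 wording, the two derivations and possibly one re-run. No new data are needed.
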